#### I. PURPOSE OF PROTOCOL

The proposed study will test the tolerability and preliminary efficacy of transcranial direct current stimulation (tDCS) combined with a cognitive training program, remotely-delivered using a telemedicine protocol in n=85 adults with multiple sclerosis (MS) and in n=30 adults with Parkinson's Disease. Overall, the enrollment goal for this study shall be n=115. The objective of this study is to establish a study protocol to use in clinical trials to evaluate the efficacy of tDCS to ameliorate two of the most debilitating symptoms of MS that remain without effective treatment: cognitive impairment and fatigue. We developed the protocol to be used for this study at our former institution, Stony Brook Medicine, and have published the results. As described below, it has been tested in n=20 adults with MS with over 192 active sessions. The tDCS administered in our protocol has been very well-tolerated (all sessions successfully completed, no side effects reported to be more than moderate level).

# II. BACKGROUND

**MS is a common disorder associated with major costs.** MS is characterized by demyelination, immune-mediated inflammation, and neurodegeneration within the central nervous system. The most common subtype is relapsing-remitting and over half of these individuals transition to a progressive course; the remainder have a progressive course from the onset. MS is the most common progressive neurologic disorder in adults of working-age. It is estimated to affect more than 2.3 million people worldwide including over 400,000 individuals in the US costing up to ~\$52,000 per patient per year .

**tDCS is a novel, safe, well-tolerated and low-cost treatment approach that strongly warrants investigation in MS.** The application of tDCS is a relatively recent therapeutic development that utilizes low amplitude direct currents to induce changes in cortical excitability. tDCS is expected to produce neuronal polarization of less than one mV . tDCS produces relatively diffuse current flow, as demonstrated by imaging studies and computational models. Most of the studies in healthy and clinical populations have used electrode montages that produce some current flow across the frontal lobe (including any montage with a supra-orbital "return"). A broad neuromodulation of the frontal pole may be consistent with a general mechanism of action for its activating effects, along with a general increase in large-scale network connectivity.

tDCS produces current intensities in the brain orders of magnitude below other stimulation techniques such as transcranial magnetic stimulation (TMS) or electroconvulsive therapy (ECT) ; tDCS has none of the significant side-effects reported with these much more intensive interventions. Many subjects feel nothing or only mild sensation during the main course of tDCS. Across studies, the most common side effect reported from this technique is a mild tingling sensation .

Though various non-invasive neuromodulation technologies are available (e.g., transcranial magnetic stimulation), tDCS has many advantages compared to other stimulation methods including ease of use, lower cost, and better tolerability (e.g., it has not been associated with development of seizures). With an extensive record of safety and tolerability, the most common side effects are specific to the

electrode site and include itching, tingling, and burning. Initial studies have found tDCS to be effective in a variety of uses in healthy participants as well as in a range of clinical conditions and may be preferred to drug treatment in special populations (such as pregnant women) due to its safety advantages.

tDCS is considered especially promising for symptomatic treatment in MS both for its tolerability, deployability (based on our innovative remotely-supervised approach), and presumed mechanism of action. While there is emerging study the cellular mechanisms of tDCS, what is established is that sustained (minutes) of tDCS can produce lasting changes in brain excitability and that these changes are plastic and cumulative with repeated sessions . One of the largest and more reproducible effects in healthy volunteers is enhanced vigilance with an increased ability to engage selective attention, a finding which may indirectly underpin the cognitive benefits of tDCS. In clinical populations, one of the most replicated measures is elevated mood and has been considered an effective treatment for depression.

We have developed a telemedicine tDCS protocol that will facilitate recruitment, increase compliance, and enable designs with multiple sessions to evaluate benefits of a cumulative effect. tDCS urgently requires further study to fully leverage this treatment modality for maximal clinical benefit in MS. Repetitive sessions are necessary to produce cumulative effects as shown in neurophysiology studies and clinical trials for neuropsychiatric disorders and rehabilitation. For the treatment of depression, a clinical application that has received extensive study, some patients have required 20 to 30 sessions or more for optimal improvement .

We believe that studies of tDCS in MS have been limited by sample size and number of treatment sessions due to the barrier of access for most MS patients to participate in studies requiring multiple consecutive clinic visits for treatment. Daily travel to a treatment facility is a real-world limitation because it is not feasible for those with a full work and family schedule (requiring time taken from meeting these other obligations), or limited mobility and/or restricted transportation options (which can be especially burdensome for caregivers). For example, all but one study of tDCS in MS to date (treating symptoms of pain, fatigue, sensory and motor functioning ) has included more than five sessions, and none have enrolled more than 31 participants (and, in this largest sample size, participants only completed one tDCS session). To study multiple applications of tDCS in MS, participants must be able to access these treatments from home.

To address this need, we have developed a remotely-supervised telemedicine protocol to provide access to tDCS treatment to participants in their homes. Our protocol was developed following our group's extensive experience with a remotely-supervised cognitive remediation program , and meets collaborative guidelines and standards that we established working with a diverse group of tDCS clinical investigators. As detailed below, our protocol is opposed to self-directed home use, where a patient is given a device without parameters and real-time supervision, which is not advisable due to both safety concerns as well as problems with uniformity and reproducibility of results. Instead, we maintain clinical trial standards for safety and consistency with a specially-designed tDCS device (that "unlocks" one "dose" per code, controlled by a study technician) with extensive checkpoints and built-in safety features for study using remote supervision through a telemedicine videoconferencing platform.

**Feasibility and safety study for our telemedicine tDCS protocol** Consistent with the demonstrated safety and tolerability across hundreds of clinical trials in tDCS, including a total of eight published trials in MS, we found very high tolerability in our feasibility study. In less than five months

*we administered 192 active tDCS* sessions in n=20 MS patients receiving 10 open-label sessions over two weeks (approaching the combined published experience of tDCS in MS fatigue). Participants have ranged in age from 30 to 69 years and included individuals with all subtypes (n=6 relapsing remitting, n=12 secondary progressive, n=2 primary progressive), and a range of disability from mild to severe or wheelchair dependent disability (EDSS scores of 1.0 to 8.0). No adverse effects or side effects of severe intensity have been reported in any session, and no session has been discontinued. As seen in **Figure 1**, the most common adverse event reported was skin tingling, and this did not exceed an intensity of "moderate."

Due to both the novelty of tDCS and the option to participate remotely, we have met great interest in our MS patient community with rapid enrollment, limited only by device and staff availability (53 patients on a waitlist over a three-month period). Compliance has been near-universal and all but one participant (95%) completed at least 8 of the 10 study sessions (this study discontinuation was due to personal family events unrelated to tDCS or the study). Further, the majority of participants have reported benefit from tDCS and requested to continue past the study's 10 sessions.

# Figure 1: Frequency of side effects reported across 192 tDCS sessions with remotely-supervised protocol

# III. SIGNIFICANCE AND BACKGROUND FOR THE STUDY

The objective of this study is to establish a study protocol to use in clinical trials to evaluate the efficacy of tDCS to ameliorate two of the most debilitating symptoms of MS that remain without effective treatment: cognitive impairment and fatigue.

# **Cognitive impairment:**

Cognitive impairment occurs frequently in MS and is without an effective treatment option: Cognitive impairment occurs in up to 70% of all patients and, in this younger adult population, is a major cause of disability leading to unemployment, social isolation, and increasing dependence on caregivers. The most common deficits are in the area of working memory (WM), measured by tests of information processing, attention, and new learning. Impairment can occur independently from other disease features and is linked to cerebral atrophy, and, in particular, regional grey matter volume loss. Unfortunately, medications have not been effective. Disease-modifying medication possibly slows the progression of deficits, but does not improve functioning. Symptomatic medications such as the

cholinesterase inhibitor donepezil (trials completed at our center) and L-amphetamine are not effective as standard treatment and can include safety concerns (e.g., potential for abuse). •Neural plasticity-based computerized cognitive training (CT) programs are promising: There has been limited study of CT in MS. Traditional approaches (e.g., clinician-delivered compensatory strategies and drill-and-practice training) are costly and difficult to uniformly implement, with inconsistent benefit. Recent technological advances have led to computer-based CT approaches. Rather than focusing on compensation, intensive repetitive targeted exercise may actually improve cognitive ability at the processing level, possibly through mechanisms of neural plasticity. This *plasticity-based* approach aims to drive change with exercise components including trials that are rapidly adapted to the individual user in real-time to maintain a consistent level of challenge. Initial studies in MS have linked cognitive reorganization with training.

We have completed two controlled trials in MS demonstrating the superiority of this type of CT compared to ordinary computer games. Our group has developed a protocol to allow participants to access CT from home, targeting 60 sessions over 12 weeks . The remote access has resulted in rapid enrollment of >160 patients in two years; in comparison, in the largest published CT trial in MS, an outpatient memory training program with10 sessions in five weeks, required >7 years to enroll n=86 participants. Using our protocol we have found very high compliance, with no loss of study equipment, weekly participant phone interviews, and all but two completing the program through the study end visit. These results emphasize the tremendous unmet treatment need for people living with MS, and have led to the established procedures to be used in this study to deliver remotely-supervised cognitive remediation.

•tDCS can increase the benefit of CT: While many questions remain, pairing tDCS with CT has increased learning and performance particularly in tasks depending on WM. Preliminary data from our recently-completed randomized double-blind active-placebo controlled trials show that CT leads to leads to greater gains in a neuropsychological testing composite z score when compared to playing ordinary computer games (n=135, program by Posit Science, p=0.02, report in preparation; and n=20, program by Lumos Lab, 0.46±0.59 improvement vs. $-0.14\pm0.48$  decline,  $p=0.02^{41}$ ). However, the difference in average improvement of the composite z-score is relatively modest, z-score 0.20±0.36 vs. 0.05±0.31, p=0.02, Cohen's d=0.43. The proposed research will take the first step towards determining whether the benefit of CT can ultimately be improved when combined with tDCS.

# Fatigue:

Fatigue is the most frequent debilitating symptom of MS and remains without an effective treatment: 75% or more of patients report it is among their most disabling MS problem, and 55% indicate it to be the worst. Defined by the subjective sense of overwhelming tiredness and exhaustion, there are serious adverse health care consequences linked to fatigue in general, and MS fatigue in particular. Fatigued MS patients leave the work force early, have increased health care utilization, and are at risk for depression. However, despite careful description (initially with the Fatigue Severity Scale or FSS, developed by study Co-I [name]), the etiology of MS fatigue remains poorly understood. MS fatigue is neither consistently linked to disease severity as measured by the Expanded Disability Status Scale or EDSS nor disease duration, although it is generally found to be worse with individuals with the secondary progressive subtype. Fatigue is distinct from sleepiness and fails to improve with adequate sleep. Multiple factors contribute to fatigue, including CNS demyelination and axonal loss, immunological changes, MS-related problems (trigeminal neuralgia, spasms), psychological and chronic illness factors (depression, pain, poor sleep), and medications.

A wide variety of therapies have been attempted for fatigue in MS but there remains no accepted or standardized treatment. Fatigue may improve with disease modifying therapy but there is no evidence of consistent benefit. No symptomatic medication, including large trials of modafinil, amantadine and pemoline , has been found to be reliably effective. Behaviorally-based management programs (e.g. cognitive behavioral therapy, mindfulness-based interventions), exercise programs and comprehensive strategies to manage MS fatigue directly have also been studied. While these treatment efforts have had somewhat more success than medications, they are costly in terms of clinician and patient time, usually require weekly or more frequent clinic visits for therapy, and are not widely available. Overall, fatigue in MS has remained frustratingly treatment-resistant. A consistently effective, reliable and accessible fatigue treatment option is greatly needed.

Of the eight published trials of tDCS to date, three have directly targeted fatigue. As shown in **Table 1**, all three have used sham-controlled crossover designs, and found significant improvement in fatigue following active treatment in either the full group or subset analyses. Each of the three studies varied in their montage with similar results.

Table 1 . tDCS studies of fatigue in MS to date, including our feasibility study and proposed study							
Author (Year)	Sample n	Design	#Sessions, Treatment Montage				
Ferrucci et al. (2014) 	25	Sham-controlled crossover	5 sessions x 1.5 mA motor cortex x 15 minutes				
Saiote et al. (2014 ) 	13	Sham-controlled crossover	5 sessions x 1.0 mA DLPC x 20 minutes				
Tecchio et al. (2014) 	10	Sham-controlled crossover	5 sessions x 1.5 mA x 15 minutes; sensorimotor cortex				
Protocol feasibility study	17	Open-label (remote protocol)	10 sessions x 1.5 mA DLPFC x 20 minutes				

Two of the three studies included analyses to link to the mechanism of benefit, with unclear results. Saiote et al. included MRI and found a correlation between lesion load in left frontal cortex and reduced fatigue following tDCS treatment. In a follow-up second analyses, Tecchio et al. found tDCS treatment was more effective against MS fatigue when the electrode was focused on the bilateral whole body somatosensory area (but changes in S1 and M1 excitability did not correspond to treatment benefit).

# IV. SPECIFIC AIMS

Specific Aim 1: To test the feasibility of a randomized, controlled remotely-supervised tDCS clinical trial protocol developed specifically for use in MS. Participants (n=85) will be randomly assigned to receive 40 x 20-minute sessions of either active (up to 2.5 mA) paired with cognitive remediation, to two separate control conditions. The first is an active tDCS condition paired with non-adaptive, traditional puzzle and board games and will act as this study's negative control. The second control will act as the study's positive control and will be sham tDCS paired with cognitive remediation. Each study session, regardless of study arm, will be followed by an additional 10 minute computerized training sessions post-stimulation. Each study arm will complete 40 sessions over eight weeks.

The *primary outcome* for feasibility will be the number of participants completing at least 80% or n=32of the targeted 40 sessions. Secondary outcomes will be comparison of tolerability and participant- reported side effects between the two treatment arms.

# **Specific Aim 2:** To test the preliminary efficacy of tDCS to treat fatigue and to enhance outcomes of cognitive training. These data will inform the design of a large, controlled clinical trial.

The *primary outcome* will be comparisons between the active and control conditions on measures of fatigue and cognitive functioning.

# V. DESCRIPTION OF THE PROTOCOL

# The goal of this pilot study is to establish a structured protocol for safe remotely-supervised delivery of 40 consecutive tDCS sessions (active and control conditions) to be used in a randomized, controlled double-blind clinical studies in participants with MS.

*a)* Study Design: Participants will complete a total of 40 sessions across eight weeks: training at baseline with a study technician and then monitoring (through secure online video) by the study technician for the remaining thirty-nine sessions. We will use the most common montage of bilateral dorsolateral prefrontal cortex (DLFPC) placement, with the anodal electrode placed on the left side. This offers ease of reliable electrode placement and wide therapeutic applications. Dose will be up to the target of 2.5 mA with reduction to 2.0, 1.5, or 1.0 mA based on tolerability testing at baseline. At study end, participants in the sham condition will be offered 10 open label active sessions.

**b)** Study Equipment: For the remotely-supervised sessions, participants will be given the speciallydesigned tDCS device and headset, study laptop computer for secure video monitoring with study technician (must have internet access), a detailed reference manual, and a training video. The Soterix mini-CT is uniquely designed for remotely-supervised delivery and requires a one-time use code provided by the study technician to unlock the device for one stimulation session. The device will not operate without correct headset placement and has a single-button option to abort the session. The device will also automatically abort the session if optimal conditions are not maintained. It reports and records a completion code for each session.

**c)** Randomization: Participants will be assigned to each condition in a 1:1:1 Stratified randomization procedure. Participants will be matched according to the degree of cognitive impairment (Symbol Digit Modalities test or SDMT score) and neurologic (motor) impairment (Expanded Disability Status Scale or EDSS score). Participants will be randomized to either the active tDCS condition paired with cognitive remediation or one of the two control conditions. The positive control condition will consist of cognitive remediation paired with sham tDCS and the negative control condition will consist of active tDCS with non-adaptive puzzle and board games using block randomization of permuted block sizes 3 and 6, based on our experience in cognitive remediation trials. SDMT performance will be categorized compared to published age-normative means (>0.99 SD, 1 to 2 SD and 2 to 3 SD below mean) and EDSS score will be categorized as mildly or moderately impaired (0 to 3.0 vs. 3.5 to 8.0).

d)*Outcome Measures:* Before and after each session, participants will complete brief measures to monitor for any stimulation-related events as well as mood and fatigue. In addition a pain scale will be administered during the session. Participants will also complete baseline and study-end inventories of mood and fatigue and complete a brief battery of cognitive tests including the Brief International Assessment of Cognition in MS or BICAMS, to help guide power estimates for the future trials. A summary of outcome measures can be found in Table 2.

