#### **Eligibility Criteria**

Enrolled participants must have a diagnosis of MS (any subtype) with stable disease status and expanded disability status scale (EDSS) scores of less than 6.5 or above with proxy. Individuals with a Symbol Digit Modalities Test or SDMT  score  $\geq$  3.0 SD below published norms will be excluded as will those with any health condition contraindicated with the use of a tDCS device (including history of seizures, abnormal EKG, skin disorders, head trauma or medical device in the head or neck). Baseline screening evaluation will include a neurological exam and medical clearance by the study physician and brief screening evaluations for ability to operate the study equipment.

Inclusion Criteria	Exclusion Criteria

 
Ages 18-79
 
Definite MS diagnosis, all subtypes [95]
 
MS-related changes in cognitive functioning*
 
A score of 6.5 or lesson the Expanded Disability Status Scale (EDSS) OR more than 6.5 with proxy
 
	
 
Visual, auditory and motor deficits that would prevent full ability to understand study instructions or operate the tDCS device or study laptop, as judged by treating neurologist or study staff
 
Relapse or steroid use in previous month
 

 
Has stable and continuous access to internet service at home compatible with the study laptop (Wi-Fi or ethernet cable)
 
Adequate internet capacity for remote monitoring, as tested by
 
	
 
History of mental retardation, pervasive developmental disorder or other neurological condition associated with cognitive impairment
 

 
http://www.speedtest.net/)
 
Adequate home facilities (enough space, access to quiet and distraction free area)
 
	
 
Primary psychiatric disorder that would influence ability to participate
 
History of seizures or seizure disorder
 

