
 
Able to commit to the two-week period of training sessions with baseline and follow-up visits.
 
Able to understand the informed consent process and provide consent to participate in the study
 
	
 
History of head trauma (e.g., head injury, brain surgery) in the past year or medical device implanted in the head (such as Deep Brain Stimulator) or in the neck (such as a Vagus Nerve Stimulator)
 
Any skin disorder/sensitive skin (e.g., eczema, severe rashes), blisters, open wounds, burn including sunburns, cuts or irritation, or other skin defects which compromise the integrity of the skin at or near stimulation locations (where electrodes are placed)
 
Treatment for a communicable skin disorder currently or over the past 12 months
 
History of uncontrolled or labile hypertension.
 
Other serious uncontrolled medical condition (e.g., cancer or acute myocardial infarction)
 
History of clinically significant abnormalities on electrocardiogram (EKG)
 
Alcohol or other substance use disorder
 
Learned English language after 12 years of age
 
Pregnant or breastfeeding
 
Symbol Digit Modalities Test ≥3.0 SD below published norms
 

---	---

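### As printed, the SDMT and EDSS randomisation strata do not give every eligible participant exactly one stratum, and the Aim 2 comparisons name no stratification factors

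*Combined protocol and SAP*

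**What the plan says.** Section V.c (Randomization) sets the allocation rule for the MS part of the trial: "Participants will be assigned to each condition in a 1:1:1 Stratified randomization procedure". The strata are formed from cognitive impairment (SDMT) and neurological impairment (EDSS), with "block randomization of permuted block sizes 3 and 6". SDMT is banded against age norms as ">0.99 SD, 1 to 2 SD and 2 to 3 SD below mean". For disability, "EDSS score will be categorized as mildly or moderately impaired (0 to 3.0 vs. 3.5 to 8.0").

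Eligibility (section VII) is wider than these bands at two points:

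- **SDMT** is limited only at the low end; the exclusion is "Symbol Digit Modalities Test ≥3.0 SD below published norms". The other cognitive criterion, "MS-related changes in cognitive functioning", carries no SDMT threshold.
- **EDSS** is described as "scores of less than 6.5 or above with proxy". The inclusion table likewise admits scores over 6.5 with a proxy. Neither place gives a maximum.

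For Aim 2, the Analytic Plan (V.e) and the Statistical Analyses part of section IX plan change scores from baseline to study end, compared between arms by t-tests and analysis of variance. Neither place names SDMT or EDSS stratum as a factor. Section IX lists clinical features for a correlational analysis, and neither variable is among them.

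**The concern.** Stratified permuted blocks work only if each participant belongs to one stratum and the rule that assigns it can be applied the same way every time. The sentence in V.c is the operative rule, and no other section redefines the bands or says how a score on a boundary or outside the bands is handled.

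At stake is balance between the three arms on cognition and disability, the two features that the plan chose to control. Cognitive change is itself an Aim 2 outcome. The stratum is also the natural covariate for that comparison. A stratum that cannot be derived from the protocol text cannot be rebuilt at analysis, and one that is left out of the model brings no gain in precision.

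**Working it through.** The plan states no figure that depends on the bands, so the check is one of coverage: how many bands contain each eligible score?

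**SDMT.** Let d be the number of SDs below the normative mean (negative if above it). Eligible scores have d < 3.0 (section VII). I took d from −3.00 to 2.99 in steps of 0.01, which gives 600 values.

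*Literal reading.* The words after the third band govern all three, so the bands are d > 0.99, 1 ≤ d ≤ 2 and 2 ≤ d ≤ 3.

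- d from −3.00 to 0.99: 400 values, all in no band.
- d from 1.00 to 2.99: 200 values, all in at least two bands. For example, d = 1.5 is in the first and second, and d = 2.0 is in all three.
- Values in exactly one band: 600 − 400 − 200 = 0.

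*Probable intent.* The first band means better than 0.99 SD below the mean, so the bands are d < 0.99, 1 ≤ d ≤ 2 and 2 ≤ d ≤ 3.

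- In no band: 1 value, d = 0.99. If the first band includes 0.99, none.
- In two bands: 1 value, d = 2.00.
- In exactly one band: 600 − 2 = 598 (599 if 0.99 is included).

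*Bands proposed below.* d < 1.0, 1.0 ≤ d < 2.0 and 2.0 ≤ d < 3.0 hold 400 + 100 + 100 = 600 values, each in exactly one band.

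**EDSS.** The documents do not define the scale. I assumed half-point steps from 1.0 up to 9.5.

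- 3.0 and 3.5 are adjacent, so there is no gap between the bands.
- 8.5, 9.0 and 9.5 are admissible with a proxy under section VII and belong to no stratum.
- With bands of 3.0 or lower and 3.5 or higher, every value has one stratum, and no score of 8.0 or below changes stratum.

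**Stratum size.** There are 3 × 2 = 6 strata. With 85 MS participants, the average is 85/6 = 14.2 per stratum, or 85/18 = 4.7 per arm per stratum. These are averages only; the documents do not give the distribution across strata.

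**The case against.** The strongest reply is that the intent is plain. A cut at 0.99 next to a band that starts at 1 makes sense only as the complement of that band, so the fault is a reversed or missing sign. Whether it lies in the protocol or arose when the file was read cannot be settled from this text. I accept the intended reading as probable. It disposes of the large overlap and the large gap, but not of the shared 2.0 SD boundary or the EDSS ceiling.

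The EDSS gap may also be rarely reached. The aptitude test (section VI) stops participants who cannot fit the sponges or electrodes, section VII excludes motor deficits that would prevent use of the device or laptop, and the feasibility sample (section II) ran from 1.0 to 8.0. This stands as to size, but none of these provisions sets an EDSS limit.

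A reader might infer three stronger things that the documents do not support:

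- **That a large share of participants would have no SDMT stratum.** This needs the implausible reading and an SDMT distribution that the documents do not give.
- **That staff would place participants at their discretion.** Section VI says only that the PI or an unblinded technician programs devices to match the randomisation. Nothing describes how strata are entered.
- **That a planned stratum-adjusted analysis is spoiled.** None is planned. The absence of the factors is a separate and smaller point about precision.

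**Conclusion.** The point holds as a defect of definition, not as a criticism of the choice of SDMT, EDSS or permuted blocks. The first SDMT band is misworded. On either reading, 2.0 SD below the mean lies in more than one band and EDSS above 8.0 lies in none. If the probable intent is what was put into the randomisation list, the practical effect is confined to scores on a boundary and to a probably small number of participants with EDSS above 8.0. The documents do not show how the list was built, so that remains to be checked. With under five participants per arm per stratum on average, even a few unclear assignments can matter within a stratum, but I would rate the point as minor.

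The lack of stratification factors in the Aim 2 comparisons does not invalidate them. If SDMT and EDSS predict change, comparisons that ignore them tend to overstate the standard error and give up precision that a pilot of this size could use. The EDSS part rests on the assumed half-point steps and upper end of the scale.

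**What to change.** 1. In V.c, replace the SDMT bands with: less than 1.0 SD below the norm (including above it); 1.0 to less than 2.0 SD below; 2.0 to less than 3.0 SD below.
2. Replace the EDSS bands with 3.0 or lower versus 3.5 or higher, so that they cover the whole range admitted in section VII.
3. Check the randomisation list against these bands, and record how any participant already randomised with a boundary or out-of-range score was assigned.
4. In V.e and section IX, add the SDMT and EDSS strata as factors in the Aim 2 analysis of variance or covariance.

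The cost is a sentence in V.c, a check of the list set-up and a line in the analysis sections. The six-stratum structure, the sample size and the eligibility rules are unchanged.
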